Even when clinicians try to prevent intraoperative hypotension, they often fail because it is difficult to predict which patients will become hypotensive, much less when. A risk score for predicting minute-by-minute intraoperative hypotension is not currently available. Yet it seems likely that ability to identify when a patient is likely to become hypotensive, and the pathophysiology of the event, will improve hemodynamic management and perhaps patient outcome. Acumen HPI appears to be a reliable predictor of intraoperative hypotension, and should thus help clinicians anticipate and avoid hypotension. Furthermore, the secondary guidance provided by the Acumen HPI may help clinicians optimally manage fluids and thus prevent future episodes in the same patient.

AIMS

To determine whether use of Acumen HPI software to guide intraoperative hemodynamic management in the non-cardiac surgery reduces the duration and severity of hypotension.

PRIMARY HYPOTHESIS

Our primary hypothesis is that use of the Acumen HPI software guidance reduces TWA intraoperative hypotension below a threshold of 65 mmHg.

Specifically, we will compare the amount of intraoperative hypotension below mean-arterial pressure (MAP) threshold of 65 mmHg, in patients randomized to invasive arterial pressure monitoring vs. invasive arterial pressure monitoring with Acumen Hypotension Prediction Index software.

OUTCOMES

Primary:

1. Time- weighted average (TWA) MAP under a threshold of 65 mmHg.

Secondary:

- 1. Time-weighted average MAP below a threshold of 60 mmHg per case;
- 2. Time-weighted average MAP below a threshold of 55 mmHg per case.

Exploratory:

- 1. A composite of non-fatal cardiac arrest, in-hospital death, stroke, and MINS;
- 2. Acute kidney injury (AKIN criteria);
- 3. Quality of recovery (QoR-15) on postoperative day 3;
- 4. Postoperative morbidity survey (POMS) on postoperative day 3;
- 5. Transfusion requirement (ml packed red blood cells);
- 6. Amounts of intraoperative crystalloid and colloid;
- 7. Amount of vasoactive phenylephrine, ephedrine, nor-epinephrine, epinephrine, dobutamine;

- 8. Advanced hemodynamic variables- Cardiac output (CO), Cardiac Index (CI), Stroke Volume (SV), Stroke Volume Variation (SVV), Dynamic elastance (Edyn);
- 9. Hospital length of stay;
- 10. Hospital readmission within 30 days.

	Outcomes	Measurements			
1. Primary	TWA MAP drop under 65 mmHg threshold	Intraoperative record form EV1000 monitor			

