To ensure efficient recruitment, research personnel will screen the patient list in the preoperative assessment clinic to identify eligible patients. Research personnel will use a variety of screening approaches to capture patients who do not attend the preoperative assessment clinic, including screening: the daily surgical list in the operating room, patients on surgical wards and intensive care units, and patients in the preoperative holding area. Center will also use all potential patient sources including asking the services of anesthesia, surgery, and medicine to page the study personnel regarding all surgical admissions through the emergency department and consultations for floor patients requiring surgery. Research personnel will approach all eligible patients to obtain informed consent. We will enroll patients undergoing surgery at single institution (Cleveland Clinic foundation, Cleveland, Ohio, USA)

DATA ANALYSES

Randomized groups will be compared on baseline variables using the standardized difference (difference in means or proportions divided by the pooled standard deviation), and such variables will be considered balanced if the absolute standardized difference is < 1.96 sqrt(2/N), where N is the per group sample size. Imbalanced variables will be adjusted for in all analyses.

The treatment effect of Acumen HPI guidance (versus no Acumen HPI guidance) on the primary outcome of intraoperative time- weighted average (TWA) MAP under a threshold of 65 mmHg will be assessed with a Wilcoxon-Mann-Whitney 2-sample 2-tailed test, or analogous test to account for imbalanced baseline variables or non-normal distribution of the outcome, as needed. Secondary and exploratory continuous outcomes will be analyzed in the same way.

Randomized groups will be compared on binary outcomes using a Pearson chi-square test or else logistic regression to adjust for baseline variables, as needed, and on oral outcomes using either the Wilcoxon Mann-Whitney test or a proportional odds logistic regression model, as appropriate.

For all analyses, focus will be on the estimated treatment effects and their confidence intervals, as well as the P-values. SAS statistical software, Carey, NC, will be used for all analyses.

SAMPLE SIZE CONSIDERATIONS

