Summary. From our a-line study [unpublished] we observed mean (SD) of area under the curve AUC-MAP<65 of 80 (127) and median [quartiles] of 24 [1, 121]. Similar to time weighted average AUC-MAP represents depth and duration of hypotension. AUC-MAP = TWA-MAP x duration of observation. The data is highly skewed, with a non-trivial proportion of zeros. Therefore, it is not appropriate to base a sample size estimate on a t-test which assumes normality. It is best based on a non-parametric test such as the Wilcoxon-Mann-Whitney test, as put forth in the preliminary protocol for the larger study. In that study we needed about 800 patients to detect a 50% reduction in the median, based on 90% power and incorporating interim analyses. For the calculations below we use 80% power. As noted below, for the current study we recommend a total sample size of 213 to detect an approximate 20% reduction in the mean of the primary outcome of AUC-MAP < 65 mmHg x min, which based on the pilot data corresponds to a Wilcoxon-Mann-Whitney probability (i.e., a c-statistic) of 0.61.

Detailed calculations. In the below Table 3, using the same calculations based on the Wilcoxon-Mann-Whitney test as in the proposal for the larger HPI trial, we present the required sample size to detect reductions or shifts in the distribution of the primary outcome (AUC-MAP < 65 mmHg x min) which are equal to various percentages (*achieved* reductions ranging from 7% to 35%) of the control group mean. The reduction is applied on a case level (i.e., for each control observation), so that a reduction of say 10% of the mean would reduce all observations by 8 mm Hg x min (0.10 x control group mean (80 mmHg x min). But if that brings an observation below zero, the value of zero is used (cannot have negative AUC!). Table 3 thus gives a top row for the *attempted* reduction (on the case level), and then the *achieved* HPI mean and median, as well as the ratio (HPI/control) of means and medians.

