Recommended Sample Size of total N=213: In the 35% attempted reduction column, a reduction of 35% of the control mean (equal to 28 mmHg x min) was *attempted* for all control cases when constructing the HPI distribution of outcomes. The *achieved* ratio of means was 0.79, indicating a 21% reduction in the mean. The achieved reduction was not the full 35% since, as expected, many of the cases reached zero instead of the full attempted reduction. This scenario also brought the HPI median (and thus the ratio of medians) to zero. The scenario requires a total of 213 patients (107 / group). The Wilcoxon-Mann-Whitney probability of 0.61 means the probability that randomly chosen HPI patient has lower AUC-MAP<65 compared to random control patient is 0.61.

Table 3: Sample size to detect various reductions in AUC-MAP<65 for HPI vs control Recommended sample size in the 35% attempted reduction column is total N=213

Assume control group median [q1,q3] = 24 [1, 121]; mean (SD) =80 (127); zeros = 27% Power=80%, alpha=0.05, no interim analyses

Attempted	10%	20%	30%	35%	40%	50%	60%	70%
Reduction*:	(8)	(16)	(24)	(28)	(32)	(40)	(48)	(56)
% of control mean								
(mmHg x min)								
Achieved reduction								
HPI group Median	16	8	0.5	0	0	0	0	0
Ratio of medians	.67	.33	.02	0	0	0	0	0
HPI group mean	75	70	66	64	62	58	55	51
Ratio of means	.93	.87	.81	.79	.77	.72	.68	.64
Total N	1511	460	261	213	187	140	115	93
WMW prob (P')	.54	.57	.60	.61	.62	.63	.65	.67
1/ WMW odds	.85	.74	.67	.64	.62	.58	.54	.50

^{*}Attempted Reduction: Amount of attempted reduction in AUC-MAP<65 for each observation, listed as percent of control MEAN and in actual units. Achieved individual reduction was less (or even zero) in some cases since true value for an individual cannot go below zero.

HPI median: median of HPI group after the induced shift

Ratio of medians: HPI median / control median (24 mmHg x min)

HPI mean: mean of HPI group after the induced shift

Ratio of means: HPI mean / control mean (80 mmHg x min)

WMW prob (P'): Wilcoxon-Mann-Whitney probability (P'). Equal to a c-statistic from logistic regression. Probability that randomly chosen HPI patient has lower AUC-MAP<65 compared to random control patient. P' = 0.50 under null hypothesis (i.e., would be achieve by guessing), and 1.0 is perfect discrimination.

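### TWA<60 and TWA<55 get the primary's test and P-values with no testing order or gate; a fixed 65-60-55 sequence would close this gap at no cost to the primary

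*Combined protocol and SAP*

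**What the plan says.** The Outcomes section lists one primary outcome (TWA MAP under 65 mmHg), two secondary outcomes ("Time-weighted average MAP below a threshold of 60 mmHg per case" and the same measure at 55 mmHg) and ten exploratory items.

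Data Analyses assigns the primary a "Wilcoxon-Mann-Whitney 2-sample 2-tailed test", or an analogous test if baseline variables are imbalanced or the distribution calls for it. The next sentence reads "Secondary and exploratory continuous outcomes will be analyzed in the same way". Binary outcomes get a Pearson chi-square test or logistic regression; ordinal outcomes get a Wilcoxon-Mann-Whitney test or a proportional odds model. For all analyses, the "focus will be on the estimated treatment effects and their confidence intervals, as well as the P-values".

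A significance level appears in one place only, above Table 3 in Sample Size Considerations: "Power=80%, alpha=0.05, no interim analyses". That line belongs to the primary's sample size. Nowhere do the documents give an order of testing, a condition on the primary result, an alpha split, or a statement that secondary P-values are descriptive.

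**The concern.** The two secondary outcomes measure the same construct as the primary at deeper cut-offs. The trial's aim is worded as reducing the duration and severity of hypotension in general and is not tied to 65 mmHg. If TWA<65 came out non-significant and TWA<60 or TWA<55 came out below 0.05, the plan gives no rule against presenting the latter as meeting that aim. A reader of the results could not tell a pre-planned confirmatory claim from one chosen among three related tests. At stake is how the secondary results may be interpreted; the primary test itself is not affected.

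**Working it through.** **Inputs from the documents.** Two-sided test (Data Analyses). Alpha 0.05, power 80%, no interim analyses (above Table 3). Design effect: a "Wilcoxon-Mann-Whitney probability (i.e., a c-statistic) of 0.61" (Sample Size Considerations). Total N = 213, 107 per group. Control AUC-MAP<65: mean 80 (SD 127), median 24, 27% zeros (Table 3).

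**Inputs assumed.** Each secondary is read at two-sided 0.05, because no other level is given. The correlation between the three test statistics is not in the documents, so a range is shown.

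**1. Reproduce the plan's figure.** Noether's formula with equal allocation is N = (z₀.₉₇₅ + z₀.₈₀)² / [12 × 0.25 × (P′ − 0.5)²]. With P′ = 0.61:

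N = (1.960 + 0.842)² / (3 × 0.11²) = 7.849 / 0.0363 = 216.2, so 217.

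The plan's 213 is within 3% of this. Power at 213 is Φ(√(3 × 213) × 0.11 − 1.960) = Φ(0.821) = 79.4%, against 80% stated. The sample size therefore rests on one test at two-sided 0.05, with nothing set aside for the other thresholds.

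**2. Error if the three thresholds are tested without a gate, with no true effect at any threshold.** If the tests were independent, the chance of at least one P < 0.05 would be 1 − 0.95³ = 14.3%. The thresholds are nested measures from one pressure trace, so independence is only an upper bound. Simulated equicorrelated normal test statistics (1,000,000 draws per row, |Z| > 1.96) give:

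| Assumed correlation | Any of 65/60/55 significant | 60 or 55 significant, 65 not |
|---|---|---|
| 0.5 | 12.5% | 7.5% |
| 0.7 | 10.9% | 5.9% |
| 0.8 | 9.8% | 4.8% |
| 0.9 | 8.4% | 3.4% |
| 0.95 | 7.3% | 2.3% |
| 1 | 5.0% | 0% |

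The middle column is the primary's own 5% plus the last column (at 0.8: 5.0 + 4.8 = 9.8). The last column is the direct measure of the harm described.

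**3. Which correlations are plausible.** As a rough guide, 240-minute MAP series were simulated from an assumed autoregressive model tuned towards the stated control distribution. It matched only approximately: simulated AUC<65 mean 68, SD 136, median 15, 27% zeros. With 107 per arm and 20,000 replicates, the correlations between test statistics were 0.94 (65 with 60), 0.87 (60 with 55) and 0.81 (65 with 55). The any-of-three error was 8.6%, and a significant secondary with a non-significant primary occurred in 3.7% of null trials. This supports 0.8 to 0.95 as the working range and makes 0.5 look low.

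**4. Error under a fixed sequence.** When 60 is tested only after 65 succeeds, and 55 only after 60 succeeds, any false claim under the global null requires the first test to be significant. The family error is therefore 5% (4.97% in the MAP model, standard error 0.15 points). A false secondary claim needs both 65 and 60 to be significant, which has a chance of 0.9% at correlation 0.5 and 3.0% at 0.9.

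**5. Cost to the primary.** With the sequence there is none: alpha 0.05, N = 213 and power 79.4% as in step 1. A Bonferroni split over three tests (alpha 0.0167) would lower power at 213 to Φ(2.781 − 2.394) = 65.0%, or require 289 patients.

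**The case against.** The plan already ranks its outcomes: one primary hypothesis, two secondary outcomes, and the rest labelled exploratory. It never says that a secondary result can establish efficacy, and it puts estimates and confidence intervals ahead of P-values. On this view all that is missing is a sentence on interpretation. A statement that the secondaries are supportive, with unadjusted P-values, would also remove the ambiguity. Much of this stands. The labels show intent, but they do not say what may be claimed at 60 or 55 mmHg after a null primary.

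Four stronger readings are tempting, and the documents do not support them.

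- A reader might infer that the primary's type I error is inflated. It is not: it stays at 5% whatever is done with the secondaries.
- A reader might infer that the plan declares each secondary tested at full alpha. It does not; 0.05 for the secondaries is an inference from silence.
- A reader might infer that every exploratory outcome gets the primary's test. The sentence covers continuous outcomes only; binary and ordinal outcomes have their own methods.
- A reader might count up the exploratory comparisons and cite a large chance of some false positive. Those outcomes are already labelled exploratory and several are related (cardiac output, cardiac index and stroke volume, for example), so such a figure would add no weight here.

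**Conclusion.** The gap is real but moderate. It concerns the two secondary thresholds: they are tested with P-values and no order, gate or adjustment. Reading each at two-sided 0.05, and with no true effect at any threshold, the chance of a false positive on at least one of the three is about 7% to 10%. The chance of a secondary success beside a failed primary is about 2% to 5%. Both ranges rest on assumed correlations of 0.95 down to 0.8; at 0.5 the figures would be 12.5% and 7.5%. The primary analysis and its sample size are sound on this point. The change should be made because it is cheap and the thresholds have a natural order.

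**What to change.** Add to Data Analyses, before the groups are unmasked to the analysis team:

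- TWA<65, TWA<60 and TWA<55 are tested in that order, each at two-sided 0.05, and confirmatory claims stop at the first non-significant result.
- Later thresholds are still reported, as estimates with confidence intervals, and labelled descriptive.
- Exploratory outcomes are reported as estimates with confidence intervals and no claim of significance.

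This costs wording only; the primary's alpha and N = 213 do not change. The downside falls on the secondaries: if TWA<65 is not significant, results at 60 and 55 mmHg are descriptive, even if the true benefit lies mainly in deeper hypotension.

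### Do a first quartile of 1 alongside 27% zeros, and an effect stated as a 20% lower mean, undermine the sample size of 213?

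*Combined protocol and SAP*

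**What the plan says.** Sample Size Considerations draws on an unpublished pilot in which "we observed mean (SD) of area under the curve AUC-MAP<65 of 80 (127) and median [quartiles] of 24 [1, 121" (closing bracket omitted). Table 3 repeats these figures as the control assumption and adds a zero share: "Assume control group median [q1,q3] = 24 [1, 121]; mean (SD) =80 (127); zeros = 27" (per cent). Its design settings are "Power=80%, alpha=0.05, no interim analyses".

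The Summary recommends 213 patients and describes the target effect as "an approximate 20% reduction in the mean of the primary outcome of AUC-MAP < 65 mmHg x min, which based on the pilot data corresponds". The value of P' given for that effect follows in the same sentence: "corresponds to a Wilcoxon-Mann-Whitney probability (i.e., a c-statistic) of 0.61". Detailed calculations explains that a fixed amount is taken from every control observation: "But if that brings an observation below zero, the value of zero is used". The paragraph on the recommended size then gives the chosen scenario: an attempted shift of 28 mmHg x min, an achieved ratio of means of 0.79, P' = 0.61 and N = 213. It adds: "This scenario also brought the HPI median (and thus the ratio of medians) to zero".

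Data Analyses names a two-sided Wilcoxon-Mann-Whitney test on the "primary outcome of intraoperative time- weighted average (TWA) MAP under a threshold of 65 mmHg".

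**The concern.** There are two grounds for doubt.

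First, a quartile of 1 and a zero share of 27% do not fit together. The zero share governs ties and floor effects once a shift is truncated at zero. If the wrong share had entered the calculation, P' could be off, and N with it.

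Second, the Summary expresses the detectable effect as a mean reduction, but the rank test responds to P'. The same mean reduction can arise in ways that give quite different P'. A reader of the Summary alone might take a null result as evidence against any 20% reduction, when the 80% power belongs to patterns with P' of about 0.61.

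**Working it through.** **1. The plan's own N.** Noether's formula with equal groups is N = (z₀.₉₇₅ + z₀.₈₀)² / [3(P' − 0.5)²], with (1.96 + 0.8416)² = 7.849.

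- P' = 0.61: 7.849 / (3 × 0.0121) = 216.2.
- N = 213: P' = 0.5 + √(7.849 / 639) = 0.6108, which prints as 0.61.
- Power at N = 213 and P' = 0.61: Φ(√639 × 0.11 − 1.96) = Φ(0.82) = 79.4%.
- 1/odds at P' = 0.6108: 0.3892 / 0.6108 = 0.637, printed as .64.

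The step from P' to N therefore holds within rounding of P'.

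**2. The quartile conflict.** Take 100 values with 27 zeros. The 25th and 26th ordered values are both zero, so the first quartile is 0. Nine sample-quantile definitions were checked for n from 10 to 2000. A positive quartile is possible only under some interpolating definitions and only for n of 30 or fewer; the SAS default never gives one. The conflict is real.

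**3. Was Table 3 built from the printed summaries?** The table suggests not.

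- In the 24 mmHg x min column the HPI median is 0.5. A control median of exactly 24 would give 0, so the value used was about 24.45 to 24.5.
- The same column prints an HPI mean of 66 and a ratio of .81, yet 66/80 = 0.825. An HPI mean of at least 65.5 with a ratio below .815 needs a control mean above 65.5 / 0.815 = 80.37, and below 80.5 if it prints as 80.

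Both point to unrounded data. That agrees with the text, which applies the shift to each control observation. On that reading q1 and the zero share describe the data and do not drive the calculation.

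**4. Is P' = 0.61 compatible with either figure?** Assumed control shapes were fitted to the printed mean, SD, median, third quartile and all eight columns of means, ratios, P' and 1/odds. Fits were found with 22% and 24% zeros (quartile printing as 1) and with 27% zeros (quartile 0), 36 in all. P' at the 28-unit shift was 0.608 to 0.611 in these fits, but matching the printed P' was a condition of acceptance. They show that 0.61 is attainable under either reading. They do not confirm it.

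**5. Same mean reduction, other patterns.** For a random 21% of patients moved to zero, with zero share z, P' = 0.79 × 0.5 + 0.21 × (1 − z/2).

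- z = 0.27: 0.395 + 0.21 × 0.865 = 0.577.
- z = 0.22: 0.395 + 0.21 × 0.89 = 0.582.

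Simulated power at 213 is 50–57%. If every value falls by 21%, the fitted shapes give P' of 0.527–0.536 and power of 10–14%. The truncated shift is not the only route to the planned value either. On an assumed shape with 27% zeros, a truncated 40-unit shift for values up to 121 plus an 8% cut above that gives a ratio of 0.79 and P' = 0.611. A mean reduction alone fixes neither P' nor N.

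**The case for a change.** The strongest argument for acting is that Table 3 calls these figures assumptions, and that P' has not been independently confirmed. If the printed P' values are ignored and assumed distributions are matched only to the summaries and the HPI means, a heuristic search at 27% zeros gives P' of about 0.587–0.606 (N about 232–349). Just under 25% zeros it gives 0.595–0.612 (N about 210–290), and at 20% zeros 0.608–0.625 (N about 167–226). At the worst of these, power at 213 would be Φ(√639 × 0.087 − 1.96) = Φ(0.24), about 59%.

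What stands is that the documents cannot prove P' = 0.61. What does not stand is that the conflict has moved it. The distribution behind 0.587 gives P' = 0.551 at a shift of 8 and 0.650 at 56, where Table 3 prints .54 and .67, so it is not the one the planners used. The ranges also run both ways around 213, and they rest on invented shapes.

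On the effect wording, the figures for other patterns are fair. But every power calculation assumes some pattern, and this plan states its own: the shift, the flooring, the achieved 21%, the zero median, and P' for every column. Data Analyses puts the focus on estimated effects and confidence intervals, so a null result need not be read through the planning summary.

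The sizing uses the area (AUC) while the test uses the time-weighted average. Ranks can differ when durations vary, but the section states how the two are related, and no effect on P' has been shown.

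**Conclusion.** No change to the plan is needed. The quartile of 1 and the 27% zeros cannot both describe the same control group, unless the pilot was very small or the term zeros includes near-zero values. This is a clerical slip that the team can settle from data it holds. Its effect on P' and power cannot be determined from the documents, and none has been demonstrated. N = 213 follows from P' = 0.61 to within about 1.5% (216 by formula, 79.4% power at 213). The statement of a roughly 20% lower mean is correct for the disclosed scenario of 28 mmHg x min truncated at zero. A sentence noting that other patterns have different power would be optional wording, not the correction of an error. The conclusion assumes that Table 3 was computed from the pilot observations, as the text describes and the rounding suggests. It would need another look only if the pilot data gave a P' materially different from 0.61.
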